9.1 Definitions

9.1.1 Adverse Event

As per the ICH Topic E2A (Clinical Safety Data Management: Definitions and Standards for Expedited Reporting), an AE is any untoward medical occurrence in a patient or clinical investigation subject administered a pharmaceutical product and which does not necessarily have a causal relationship with this treatment. An AE can, therefore, be any unfavorable and unintended sign (including an abnormal, clinically significant laboratory finding), symptom, or disease temporally associated with the use of a medicinal (investigational) product, whether or not considered related to the medicinal (investigational) product.

The period of observation for AEs extends from the time the subject gives informed consent until the end of study (see [Section 9.4](#) for further details).

AEs may include:

- Exacerbation (ie, an increase in the frequency or severity) of a preexisting condition. Illness present before study entry should be recorded in the medical history section of the CRF and only be reported as an AE if there is an increase in the frequency or severity of the condition during the study.
- A clinical event occurring after consent but before investigational product administration.
- Intercurrent illnesses with an onset after administration of investigational product.

AEs do not include:

- Events identified at screening that meet exclusion criteria.
- Medical or surgical procedures (the condition that leads to the procedure is the AE).
- Situations where an untoward medical occurrence has not taken place. For example:

-
- Planned hospitalizations due to pre-existing conditions, which have not worsened.
 - Hospitalizations that occur for procedures not due to an AE (eg, cosmetic surgery).
 - Hospitalizations for a diagnostic procedure where the hospital stay is less than 24 hours in duration or for normal management procedures (eg, chemotherapy).
 - Overdose of investigational product or any concomitant therapy that does not result in any adverse signs or symptoms.

For laboratory safety parameters, any instances of absolute values being outside the reference range or changes at any visit after study start that are considered by the investigator as clinically significant must be recorded in the CRF as AEs. In addition, at the investigator's discretion, any changes or trends over time in laboratory parameters can be recorded in the CRF as AEs if such changes or trends are considered to be clinically relevant, even if the absolute values are within the reference range.

Laboratory findings do not need to be reported as AEs in the following cases:

- Laboratory parameters already beyond the reference range at screening, unless a further increase / decrease can be considered an exacerbation of a preexisting condition.
- Abnormal laboratory parameters caused by mechanical or physical influences on the blood sample (eg, in vitro hemolysis) and flagged as such by the laboratory in the laboratory report.
- Abnormal parameters that are obviously biologically implausible (eg, values that are incompatible with life or outside the measuring range).
- An abnormal laboratory value that cannot be confirmed after repeat analysis, preferably in the same laboratory (ie, the previous result could be marked as not valid and should not necessarily be reported as an AE).

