2.2.2 Secondary Endpoints

Secondary Objective	Endpoint	Summary Measure(s)
Efficacy Endpoints		
1	Time-normalized number of HAE attacks	The time-normalized number (per month and year) of HAE attacks for the run-in and Treatment period.
1	The reduction in the attack rate during the Treatment Period compared to the Run-in Period	The percentage reduction and the number of subjects experiencing at least $\geq 50\%$, $\geq 70\%$, $\geq 90\%$ or equal to 100% (attack free) reduction in the time-normalized number of HAE attacks on Treatment compared to Run-in Period.
1	The time-normalized number of HAE attacks requiring on-demand treatment	The time-normalized number (per month and year) of HAE attacks requiring on-demand treatment in subjects on treatment.
1	The time-normalized number of moderate and / or severe HAE attacks	The time-normalized number (per month and year) of moderate and / or severe HAE attacks in subjects on treatment.
1	SGART	Number and percentage of subjects rating their response to therapy as good or excellent.

Secondary Objective	Endpoint	Summary Measure(s)
Safety Endpoints		
2	
 • SAEs • Deaths • Related TEAEs • TEAEs leading to study discontinuation • TEAEs by severity • Anti-CSL312 antibodies • Laboratory findings reported as an AE • AESIs (ie, thromboembolic events, abnormal bleeding events, severe hypersensitivity, including anaphylaxis events) • TEAE (for nC1-INH subjects only) 	The number and percentage of subjects experiencing the specified safety events on treatment with CSL312.

AE = adverse event; AESI = adverse event of special interest; nC1-INH = normal C1-esterase inhibitor; SAE = serious adverse event; SGART = Subject's Global Assessment of Response to Therapy; TEAE = treatment-emergent adverse event.

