3.3.2 Dose Rationale

The 200 mg dose is the dose used in Study CSL312_3001, the pivotal phase 3 study, and will continue to be evaluated in this study. The dose of 200 mg was selected based on the efficacy and safety observed in TP1 of Study CSL312_2001, CSL312 PK, inhibition of FXIIa-mediated kallikrein activity, and exposure-response (E-R) modeling.

The 200 mg dose was highly effective across various efficacy endpoints and had a favorable safety profile. In addition, the 200 mg dose resulted in ~50% inhibition of FXIIa-mediated kallikrein activity.

To support phase 3 dose selection, an E-R model was used to simulate HAE attack rates over a wide range of CSL312 concentrations that would be expected after different dosing

regimens. Based on the E-R model, the estimated daily average concentrations to achieve 50, 75, and 90% relative risk reduction in the baseline attack rate were 1.4, 3.3, and 7.8 µg/mL, respectively. The median predicted minimum daily average CSL312 concentrations ($C_{avg,min}$) at steady-state following 200 mg SC once monthly regimen corresponds to the 90% relative risk reduction in baseline attack rate in 73% of patients.

Additionally, the E-R model showed a cumulative effect of CSL312 concentration is evidenced in the reduction in the expected number of HAE attacks per month. The 200 mg SC once monthly regimen is predicted to reduce the mean attack rate by approximately 91% compared to placebo. Increasing the dose beyond 200 mg is not predicted to result in significant further reductions in HAE attacks.

Finally, the exposures at the 200 mg SC dose administered monthly are not expected to cause activated partial thromboplastin time prolongation in the majority of subjects in the phase 3 study.

Based on all the factors taken into consideration in selecting a dose for advancing the CSL312 clinical program, a 200 mg SC dose of CSL312 administered once monthly is expected to achieve clinically meaningful treatment effect and optimal benefit / risk ratio in subjects with HAE.

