10.3 Statistical Analyses and Methods

Analysis datasets will be created according to Clinical Data Interchange Standards Consortium (CDISC) standards, and data will be displayed according to reporting standards described in the SAP.

Continuous variables will be described by the number of observations, mean values with their 95% confidence intervals (CIs), SD, 25th percentile, median (50th percentile), 75% percentile, and range (minimum to maximum). The geometric coefficient of variation will be expressed as a percentage for PK and PD data and will be calculated as $100 \times \sqrt{\exp(\text{SD}_{\log}^2) - 1}$. The geometric mean and its 90% CI will be calculated for PK and PD data. The geometric mean and its 90% CI will be calculated by log-transforming the data, calculating the mean and the lower and upper limits of the 90% CI of the log-transformed data, and subsequently back transforming the mean and the lower and upper limits. Categorical variables will be summarized using frequency counts and percentages.

No hypothesis testing is planned for this study.

As it is expected that the coronavirus disease 2019 (COVID-19) pandemic is still ongoing during the conduct of the study, it will be assessed for subjects who are affected by COVID-19 during their participation in the study if they will be excluded from some analyses.

Reasons for an exclusion will be documented. The impact of COVID-19 will be summarized. Listings of COVID-19-associated AEs will be provided for any AEs. Treatment-emergent adverse events (TEAEs) occurring or not occurring within 7 days of a COVID-19 vaccination will be summarized. Concomitant medications used to treat COVID-19-associated AEs will be flagged. COVID-19 vaccinations will be assessed. COVID-19-related protocol deviations will be summarized, and all COVID-19-related protocol deviations will appear in the listing of protocol deviations and will be flagged. All protocol deviations will be reviewed during the Data Review Meeting.

A complete description of the statistical analyses and methods will be available in an SAP, which will be finalized before the database is locked.

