11.5 Clinical Laboratory Evaluations

The laboratory tests in Section 8.1.1 of the protocol will be summarized as described in this section. Unscheduled visits will be handled as described in [Section 8.2.5](#). Definition of the baseline assessment is in [Section 8.2.3](#).

The test names and units from the central laboratory transfer will be used. The sequence and groupings in which parameters are provided will match Table 2 of the protocol.

Separate summary tables for hematology, biochemistry, coagulation, urinalysis, and immunogenicity tests will be produced.

Summaries to be produced are:

- Laboratory values and changes from baseline by scheduled study visit for continuous tests and number and percentages per category for categorical tests.
- The number and percentage of subjects with clinically significant laboratory findings reported as AEs by test and visit. Those will be identified through the eCRF form ‘Clinical Significant Safety Lab Data.’.

The percentages for categorical tests will be based on the number of subjects with non-missing values at each visit.

The presence of anti-CSL312 antibodies will be summarized descriptively by visit. This summary will include the number and percentage of subjects who experience anti-drug antibodies.

A laboratory value that is outside the reference range is either high abnormal (value above the upper limit of the normal [ULN] reference range) or low abnormal (value below the lower limit of the normal [LLN] reference range). An abnormal laboratory value is not necessarily of potential clinical interest.

Listings of laboratory data will include test name and unit along with normal range, the sampling date and time, the test result, an assessment whether the result is high (above normal range) or low (below normal range). Any comments to the laboratory test will be provided in a separate listing, if applicable.

A by-subject listing for laboratory abnormalities will be provided in the same format as the laboratory listings described above but only containing information about abnormal laboratory results and including the laboratory category.

Listings to be produced are:

- All laboratory values including flags for values outside the normal range.
- Laboratory data for subjects with values outside the normal range.

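### Protocol 9.1.1 treats a result beyond the assay's measuring range as an example of an implausible value, so a genuine over-limit laboratory finding need not be reported as an AE

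*Protocol*

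**What the plan says.** Protocol 9.1.1 opens with a general rule for laboratory safety parameters. Values outside the reference range, or changes after study start, "that are considered by the investigator as clinically significant must be recorded in the CRF as AEs". It then lists four situations in which reporting as an AE is not required. Three matter here:

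- Artefacts from mechanical or physical effects on the sample, such as in vitro hemolysis, provided the laboratory has flagged them in its report.
- "Abnormal parameters that are obviously biologically implausible (eg, values that are incompatible with life or outside the measuring range". No laboratory flag is required.
- "An abnormal laboratory value that cannot be confirmed after repeat analysis, preferably in the same laboratory". Such a result may be marked not valid, and reporting is then left open.

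Two sets of counts depend on this reporting. The primary endpoint is TEAEs (Protocol 2.1.2). One secondary safety endpoint is "Laboratory findings reported as an AE" (Protocol 2.2.2), tabulated under SAP 11.4. SAP 11.5 adds a related summary: "The number and percentage of subjects with clinically significant laboratory findings reported as AEs by test and visit". The coagulation panel in Protocol 8.1.1, Table 2, includes aPTT and D-dimer.

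**The concern.** Incompatibility with life is a statement about the patient, and a fair test of implausibility. Lying outside the measuring range is a statement about the assay. When a true concentration or clotting time exceeds what the assay can quantify, the laboratory can only report it as above its limit. Naming that situation as an instance of implausibility puts a possibly genuine high result in the same class as an error.

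The tests for which this matters most are close to the drug's mechanism and to the thromboembolic and bleeding AESIs. The study is open-label and single-arm, so its safety conclusions rest on descriptive AE counts. Any omission under this rule can only lower those counts.

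**Working it through.** There is no power or sample-size figure behind this rule to reproduce (Protocol 10.3: "No hypothesis testing is planned for this study"). The check is to apply the two rules to one value and then trace where that value would appear.

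**Step 1: one value, two rules.** Take a D-dimer or aPTT reported as above the upper measuring limit. Assume that this limit lies above the upper reference limit; the documents do not give either.

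- General rule: the value is outside the reference range, so if the investigator judges it clinically significant it must be recorded as an AE.
- Exemption: the value is outside the measuring range, which is a named example of the implausible class, so it need not be reported.

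Both apply to the same result, and a site following the exemption is within the protocol.

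**Step 2: does the governing condition prevent this?** The exemption formally covers only obviously implausible values. But the example tells the site that an over-limit result is one, and nothing asks for a separate plausibility check or a laboratory flag. The hemolysis item shows that the authors knew how to add such a safeguard.

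**Step 3: where an unreported over-limit value would still be seen.**

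- Laboratory listings (SAP 11.5): yes. All values are listed with range flags, and abnormal results have their own listing.
- Visit summaries for continuous tests (SAP 11.5): unclear. The SAP gives a rule for values below quantification for PK (SAP 12.1), but none for safety results beyond an assay limit.
- Repeats (SAP 8.2.5): if the test was repeated for safety or for an unknown reason, the initial value is used. If it was repeated for a technical problem, the valid one is used.
- Counts of subjects: no. The SAP 11.5 count is drawn from a dedicated eCRF form but defined as findings reported as AEs. SAP 11.5 specifies no count of subjects with abnormal continuous values that does not depend on AE reporting.
- AESIs (Protocol 9.1.3): only if there is a clinical event. The SMQ search in SAP 11.2 classifies coded AEs, so it would not recover a laboratory value that never became one.

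The exposed case is therefore an isolated laboratory finding, without a clinical event, that the investigator considers clinically significant but does not report.

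**Step 4: size.** The documents give no assay limits, so the number of affected results cannot be computed. The nearest figure is the sizing statement in Protocol 10.1 (100 subjects, 3%, 95%), which reproduces as 1 − 0.97^100 = 0.952. If a share f of findings with a true 3% frequency went unreported, the chance of seeing at least one among 100 subjects would be 1 − (1 − 0.03 × (1 − f))^100:

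- f = 10%: 1 − 0.973^100 = 0.935
- f = 25%: 1 − 0.9775^100 = 0.897
- f = 50%: 1 − 0.985^100 = 0.779

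The shares are assumptions. These numbers show the direction of the effect, and would hold for under-reporting from any cause.

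**The case against.** The strongest reply is that the text, read sensibly, already works. The exemption is governed by obvious implausibility, so a credible over-limit result falls outside it. The list is permissive, so the investigator may still report. A general rule with listed exceptions is not a contradiction, and the two sentences refer to different ranges (reference and measuring). A known diagnosis is recorded in preference to a laboratory finding (Protocol 9.6.1), so an extreme D-dimer accompanying a thrombosis enters as the thrombosis. AESIs are reported on an expedited basis (Protocol 9.6.2), and physical examinations include a check for deep vein thrombosis. For aPTT, Protocol 3.3.2 says that exposures at this dose "are not expected to cause activated partial thromboplastin time prolongation in the majority of subjects".

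Most of this stands and limits the point. It does not repair the example, which leads a site away from the sensible reading. The aPTT statement concerns the majority of subjects and does not rule out individual cases.

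A reader might also infer that the repeat item exempts a true transient abnormality because a later sample is normal. The documents do not support that as the natural reading. The item speaks of repeat analysis, preferably in the same laboratory, and of marking a result not valid, which is the language of analytical error. New draws are described elsewhere as repeat sampling or samples (Protocol 8.1.1, Laboratory Parameters, and 8.3). The item is also discretionary and has no special connection with extreme values. At most, the term is undefined.

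**Conclusion.** The point holds in a limited form. One example in Protocol 9.1.1 lets a clinically significant over-limit laboratory result go unreported as an AE, although the general rule in the same section would require it to be recorded. The exposed counts are TEAEs and laboratory findings reported as AEs, and any error is towards fewer events. For the primary subject count, it matters only if the subject has no other TEAE.

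A reader might go further and conclude that the most extreme coagulation results drop out of the safety data. The documents do not support this: values remain in the listings, safety repeats keep the initial measurement, clinical events are captured as AESIs, and sites remain free to report. Nor do they support any estimate of frequency. The conclusion assumes that some assays have an upper measuring limit above the reference range and that some sites take the example literally. It is a wording defect that is cheap to correct, with an unknown and probably small effect.

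**What to change.** In Protocol 9.1.1, or in the CRF completion guidance, delete the measuring-range example. Alternatively, restrict it to results the laboratory flags as erroneous, as the hemolysis item already does. Over-limit results are then assessed for clinical significance like any other out-of-range value.

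Timing matters. The Amendment 1 schedule places End of Treatment no later than September 2025, and SAP version 2.0 is dated 02 Oct 2025, so new protocol wording may come too late to affect collection. In that case, list all safety laboratory results reported beyond an assay limit and query their clinical-significance assessment before database lock. A sentence in SAP 11.5 on how such results enter the continuous summaries would complete this.

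As a secondary clarification only, state that repeat analysis means re-testing the same sample or a result the laboratory has invalidated, consistent with SAP 8.2.5.

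The cost is one or two lines of text, or one listing and a round of queries, and a few more laboratory AEs, some of which may prove unimportant.

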9.1.2 Serious Adverse Event

An SAE is defined as any untoward medical occurrence that at any dose:

- **Results in death** – The event must be the cause of death for the SAE to meet this serious criterion.

-
- **Is life-threatening** – The term “life-threatening” refers to an event in which the subject was at risk of death at the time of the event; it does not refer to an event that hypothetically might have caused death if it had been more severe.
 - **Requires inpatient hospitalization or prolongation of existing hospitalization** – the Sponsor considers “hospitalization or prolongation of existing hospitalization” for at least 24 hours as the defining criterion for an SAE. Hospital admissions for planned surgery or for normal disease management procedures (eg, chemotherapy) are not considered as defining criteria for SAEs.
 - **Results in persistent or significant disability or incapacity.**
 - **Is a congenital anomaly or birth defect.**
 - **Is medically significant** – A medically significant event is defined as an event that does not necessarily meet any of the SAE criteria, but which is judged by a physician to potentially jeopardize the subject or require medical or surgical intervention to prevent one of the above outcomes listed as an SAE criterion.

Adverse events that do not fall into the above categories are defined as nonserious AEs.

9.1.3 Adverse Event of Special Interest

There are several AEs that will be monitored as AESIs to enable an adequate risk-benefit evaluation of CSL312.

The following events will be considered AESIs:

- Thromboembolic events
 - Non-systemic thrombosis (eg, localized thrombosis associated with vascular access) is not considered an AESI
- Bleeding events that are abnormal in the opinion of the investigator
- Severe hypersensitivity, including anaphylaxis

The reporting requirements for AESIs are detailed in [Section 9.6.2](#)

9.2 Severity of Adverse Events

The severity of each AE (ie, nonserious and serious AEs) is to be assessed by the investigator as follows:

Severity	Definition
Mild	A type of AE that is usually transient and may require only minimal treatment or therapeutic intervention. The event does not generally interfere with usual activities of daily living.
Moderate	A type of AE that is usually alleviated with additional specific therapeutic intervention. The event interferes with usual activities of daily living, causing discomfort but poses no significant or permanent risk of harm to the subject.
Severe	A type of AE that interrupts usual activities of daily living, or significantly affects clinical status, or may require intensive therapeutic intervention.

Source: CDISC SDTM Severity Intensity Scale for Adverse Event Terminology.

9.3 Causality of Adverse Events

The causal relationship of an AE to investigational product, the medical device (constituent), or the combination of device and investigational product, **must always be assessed** by the investigator. All AEs will be classified as either **related** or **not related** to investigational product, the medical device (constituent), or the combination of device and investigational product. If a causality assessment is not provided for an AE (including an SAE), that AE will be considered related to investigational product, the medical device (constituent), or the combination of device and investigational product.

The degree of certainty with which an AE is attributed to investigational product or an alternative cause (eg, natural history of the underlying disease, concomitant therapy) will be determined by how well the event can be understood in terms of:

- Known pharmacology of investigational product.
- Clinically and / or pathophysiologically plausible context.
- Reaction of a similar nature previously observed with similar products, or reported in the literature for similar products as being product related (eg, headache, facial flushing, pallor).

- Plausibility supported by the temporal relationship (eg, the event being related by time to administration or termination of treatment with investigational product, drug withdrawal or reproduced on rechallenge).

